**Table 06-1 Management of immune related pneumonitis**

CTCAE v5.0 Grade	KN046 Dosing Management	Action and Guidelines	Diagnostic Consideration
Grade 1 Asymptomatic. Radiographic changes only presenting as ground glass change, non-specific interstitial pneumonia	
 
Consider delay KN046 treatment
 
	
 
Monitor symptoms and signs every 2~3 days
 
Radiologic findings should be followed on serial imaging studies at least every 3 weeks
 
Consider pulmonary consultation. Perform bronchoscopy if clinically indicated
 
	All attempts should be made to rule out other causes such as metastatic disease, bacterial (eg, Legionella, Mycoplasma) or viral infection
Grade 2 Mild/moderate new symptoms of dyspnea, cough, chest pain	
 
Withhold KN046
 
Treatment with KN046 may be resumed if the event improves to <math>\leq</math>Grade 1 within 12 weeks and corticosteroids have been reduced to the equivalent of methylprednisolone 10 mg/day orally or less
 
Discontinue KN046 if upon rechallenge the patient develops a second episode of <math>\geq</math>Grade 2 pneumonia
 
Discontinue KN046 if Grade 2 pneumonia lasting for <math>\geq</math>4 weeks despite appropriate medical intervention
 
	
 
Rule out other causes such as infectious diseases
 
Consider pulmonary function tests
 
Consider pulmonary consultation. Perform bronchoscopy and biopsy/bronchoalveolar lavage (BAL) if clinically indicated
 
Start empirical antibiotics treatment if suspicion of infection (fever, CRP increased, neutrophil counts increased)
 
Consider hospitalization and monitor signs and symptoms every day
 
If no evidence of infection or no improvement in signs and symptoms with antibiotics after 48 hours, add in prednisolone 1 mg/kg/day (or equivalent) orally with prolonged
 
	

CTCAE v5.0 Grade	KN046 Management	Dosing	Action and Guidelines	Diagnostic Consideration
			taper lasting for at least 4 weeks	
Grade 3-4 Severe new symptoms; new/worsening hypoxia; life threatening; difficulty in breathing; acute respiratory distress syndrome (ARDS)		• Discontinue KN046	
 
• Perform pulmonary function tests
 
• Pulmonary consultation. Recommend to perform bronchoscopy and biopsy/bronchoalveolar lavage (BAL)
 
• Treat with intravenous (IV) methylprednisolone 2~4 mg/kg/day (or equivalent). When symptoms improve to Grade 1 or less, a high-dose oral steroid (eg, prednisone 1~2 mg/kg/day or equivalent) taper should be started and continued over no less than 4 weeks
 
• If IV steroids followed by high-dose oral steroids does not reduce initial symptoms within 48~72 hours, treat with infliximab at 5 mg/kg once every 2 weeks. Discontinue infliximab upon symptom relief and initiate a prolonged steroid taper over 6~8 weeks. If symptoms worsen during steroid reduction, initiate a retapering of steroid starting at a higher dose of 80 or 100 mg followed by a more prolonged taper with or without administration of infliximab. Addition of mycophenolate mofetil to replace infliximab could
 
	

CTCAE v5.0 Grade	KN046 Management	Dosing	Action and Guidelines	Diagnostic Consideration
			
be considered if the subject has liver injury
 
 
• Add prophylactic antibiotics for preventing opportunistic infections
 
	

**Table 0-2** *Management of immune related colitis*

CTCAE v5.0 Grade	KN046 Management	Dosing	Action and Guidelines	Diagnostic Consideration
Grade 1 < 4 liquid stools per day over baseline		
 
• No change in KN046 dose
 
	
 
• For diarrhea, treat symptomatically (loperamide, oral hydration, electrolyte substitution, ADA colitis diet and avoid high fiber high lactose diet)
 
• Grade 1 diarrhea that persist for > 1 week should be treated with the addition of oral diphenoxylate hydrochloride and atropine sulfate four times daily and budesonide 9 mg daily
 
• Grade 1 diarrhea that persist for > 2 weeks should consider to add treatment with prednisolone 0.5~1 mg/kg (non-enteric coated)
 
• If diarrhea persists, endoscopy is recommended
 
	All attempts should be made to rule out other causes such as metastatic disease, bacterial or parasitic infection, viral gastroenteritis, or the first manifestation of an inflammatory bowel disease by examination for stool leukocytes, stool cultures, and a Clostridium difficile titer
Grade 2 4~6 liquid stools per day over baseline, or abdominal pain, or blood in stool or nausea or nocturnal episodes		
 
• Withhold KN046 till ≤ Grade 1
 
	
 
• Consultation with gastroenterologist and endoscopy is recommended to confirm or rule out colitis for Grade 2 diarrhea that persists > 1 week or Grade 1~2
 
	

CTCAE v5.0 Grade	KN046 Management	Dosing	Action and Guidelines	Diagnostic Consideration
			
diarrhea with rectal bleeding
 
 
Grade 2 diarrhea should be treated with the addition of oral diphenoxylate hydrochloride and atropine sulfate four times daily and budesonide 9 mg daily
 
Grade 2 diarrhea that persists > 1 week or Grade 2 diarrhea with diffuse ulceration and bleeding seen on endoscopy is recommended to add oral prednisolone 0.5~1 mg/kg (or equivalent) with prolonged taper lasting for at least 4 weeks prednisolone. Diffuse ulceration and bleeding seen on endoscopy represents an increased risk for the development of bowel perforation and indicates longer taper of steroid
 
	
Grade 3-4 ≥7 liquid stools per day or life-threatening		
 
Withhold KN046 
 
KN046 will be permanently discontinued if ≥Grade 3 colitis is confirmed
 
Discontinue KN046 if unable to reduce corticosteroid dose to < 10 mg per day prednisone or equivalent within 12 weeks of toxicity
 
 
 
	
 
Require hospitalization
 
Endoscopy is recommended to confirm or rule out colitis
 
Grade 3-4 colitis 
 
Systemic corticosteroids should be initiated at a dose of 1~2 mg/kg/day of prednisone or equivalent. When symptoms improve to Grade 1 or less, corticosteroid taper should be started and continued over at least 4 weeks
 
 
 
Grade 3-4 diarrhea
 
	

CTCAE v5.0 Grade	KN046 Management	Dosing	Action and Guidelines	Diagnostic Consideration
			
 
Rule out bowel perforation. Imaging with plain films or computed tomography (CT) can be useful
 
Consider consultation with gastroenterologist and confirmation biopsy with endoscopy
 
Treat with intravenous (IV) steroids (methylprednisolone 125 mg) followed by high-dose oral steroids (prednisone 1~2 mg/kg once per day or equivalent). When symptoms improve to Grade 1 or less, steroid taper should be started and continued over no less than 4 weeks. Taper over 6~8 weeks in patients with diffuse and severe ulceration and/or bleeding
 
If IV steroids followed by high-dose oral steroids does not reduce initial symptoms within 48~72 hours, consider treatment with infliximab upon symptom relief and initiate a prolonged steroid taper over 6~8 weeks. If symptoms worsen during steroid reduction, initiate a retapering of steroids starting at a higher dose of
 
	

CTCAE v5.0 Grade	KN046 Management	Dosing	Action and Guidelines	Diagnostic Consideration
			
80 or 100 mg followed by a more prolonged taper with or without administration of infliximab. Caution: infliximab is contraindicated in patients with bowel perforation or sepsis
 

• If symptoms persist despite the above treatment, a surgical consult should be obtained

	

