In Phase I data of KN046-CHN-001, the most frequently observed TRAEs was rash reported in 30 subjects (34.1%), followed by pruritus in 28 subjects (31.8%), alanine aminotransferase increased (ALT) in 17 subjects (19.3%), fatigue in 15 subjects (17.0%), infusion related reaction in 15 subjects (17.0%), aspartate aminotransferase (AST) increased in 12 subjects (13.6%), pyrexia in 11 subjects (12.5%) and arthralgia in 9 subjects (10.2%). 9 of the 88 subjects (10.2%) experienced at least one  $\geq$ Grade 3 TRAEs. Similar to the results of the KN046-AUS-001 trial, neither the treatment-related adverse events nor the irAEs in the dose escalation study of the KN046-CHN-001 trial were found to occur in a dose-dependent manner.

Management of irAEs include withholding KN046 until resolution of toxicity to Grade 1 or less. If toxicity is Grade 3 or more, steroids may be used. Further details for management can be found in Section Appendix A.

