**16. Appendix A: Guidelines on the management of immune related adverse events**

Only the general principles of treatment for relatively common immune-related adverse events are listed below. Other immune-related toxicities, including rare but severe immune-related toxicity treatments (such as immune-related ocular toxicity and central nervous system toxicity) can be found in ESMO (31) and NCCN (32). Subjects who have been treated for more than 3 weeks with steroids recommend the use of drugs such as sulfamethoxazole/trimethoprim to prevent opportunistic infections such as pneumocystis.

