CTCAE v5.0 Grade	KN046 Dosing Management	Action and Guidelines	Diagnostic Consideration
Grade 1 

ALT or AST>1-3 x ULN

Subjects with baseline ALT or AST increased, toxicity Grading worsened for <math>\leq 1</math>

	

No change in KN046 dose

	

Weekly monitor liver function tests

	All attempts should be made to rule out other causes such as medications (eg, statins, antibiotics), alcohol history, viral infections (eg, anti-HAV/HBV/HCV antibody, HEV PCR), other liver diseases (eg, anti-ANA / SMA / LKM / SLA / LP / LCI, iron studies) or metastasis / clot
Grade 2 

ALT or AST 3-5 x ULN

Subjects with baseline ALT or AST increased, toxicity Grading worsened for <math>\leq 1</math> and <math>\leq 5</math> x ULN

	

Withhold KN046

	

Monitor liver function tests every 3 days

If no improvement in liver function tests, treat with oral steroids (prednisolone 1 mg/kg/ day)

	
Grade 3-4 

ALT or AST >5 x ULN

With or without total bilirubin increased > 3x ULN

	

Discontinue KN046

	

Liver biopsy to establish etiology of hepatic injury, if necessary

Treat with high-dose IV prednisolone 2 mg/kg/day or equivalent for 24~48 hours. When symptoms improve to Grade 1 or less, a steroid taper with oral prednisone at 1~2 mg/kg/day (or equivalent) should be started and continue over no less than 4 weeks

	

		
 
• If serum transaminase levels do not decrease 48 hours after initiation of systemic steroids, oral mycophenolate mofetil 500 mg every 12 hours may be given. Caution: infliximab is not recommended due to its potential for hepatotoxicity
 
• Several courses of steroid tapering may be necessary as symptoms may worsen when the steroid dose is decreased
 
	
--	--	---	--

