Grade 1 

Abnormal in cardiac tests (eg, myocardial enzymes, ECG)

	

Discontinue KN046

	

Cardiology consultation

Exam ECG, troponin, BNP, cardiac ultrasound and chest X-ray

Immediately initiate high-dose steroid treatment

Prednisolone 1~2 mg/kg/day or equivalent

Increase steroid dose (eg, methylprednisolone 1 g/day) and add in infliximab, mycophenolate mofetil or anti-thymocyte globulin if symptoms do not promptly respond to steroids

Treat cardiovascular symptoms according to ACC/AHA guidelines

Subjects with troponin or conduction abnormalities requires to be treated within cardiac ICU

	All attempts should be made to rule out myocardial infarction, viral myocarditis, infectious heart valve disease etc
Grade 2 

Abnormal in cardiac tests with mild symptoms

			
Grade 3-4 

Moderate to severe cardiac dysfunction requiring intravenous treatment or life-threatening

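### The Grade 3-4 colitis table ties infliximab to symptom relief, although the step is for patients whose symptoms steroids have not relieved

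*Combined protocol and SAP*

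**What the plan says.** The Grade 3-4 row of Table 0-2 in Appendix A covers hospitalised patients with severe or life-threatening diarrhea or colitis. Intravenous steroids are followed by high-dose oral steroids. If that treatment "does not reduce initial symptoms within 48~72 hours, consider treatment with infliximab upon symptom relief and initiate a prolonged steroid taper over 6~8 weeks", the patient is in the second-line step. No infliximab dose or interval is given.

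The Grade 3-4 row of Table 06-1 (pneumonitis) has the same opening condition. There, if steroid treatment "does not reduce initial symptoms within 48~72 hours, treat with infliximab at 5 mg/kg once every 2 weeks. Discontinue infliximab upon symptom relief", the taper of 6 to 8 weeks follows.

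Section 2.4.1.1 goes no further than steroids and refers the reader on: "If toxicity is Grade 3 or more, steroids may be used. Further details for management can be found in Section Appendix A". Section 7.5 and the closing sentence of Table 7-1 also point to Appendix A. The introduction to Appendix A sends the reader to outside guidelines for a different group: "Other immune-related toxicities, including rare but severe immune-related toxicity treatments". Colitis is not in that group, because it has its own table.

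**The concern.** The condition for entering the step and the timing of its treatment contradict each other. Patients reach it because steroids have failed over 48 to 72 hours, but infliximab is then to be considered when symptoms are relieved. Followed literally, the cell holds back second-line treatment from the non-responders it is meant for and offers it to patients who have already improved.

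This is an operative safety instruction for seriously ill patients on a drug that blocks both PD-L1 and CTLA-4, and Section 2.4.1 lists immune-related events as an important identified risk. What is at stake is a possible misreading at the bedside. Neither the efficacy analysis nor any operating characteristic of the design is involved.

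**Working it through.** No rate, power or error calculation applies. The check is a comparison of text.

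**1. The two parallel instructions.** I compared the colitis and pneumonitis cells word by word, from the steroid-failure condition to the end of the re-taper sentence, joining the colitis text across its page break.

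| | Pneumonitis (Table 06-1) | Colitis (Table 0-2) |
|---|---|---|
| Trigger | No reduction of symptoms in 48 to 72 hours on steroids | Same |
| Action on trigger | Treat with infliximab, dose and interval given | Consider infliximab, no dose or interval |
| Role of symptom relief | Point at which infliximab stops | Point at which infliximab is considered |
| Taper of 6 to 8 weeks | After infliximab stops | Joined to the infliximab instruction |
| Words in the instruction | 73 | 65 |

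There are three differences:
- The verb treat becomes the two words consider treatment.
- Nine words are absent from the colitis cell: the dose and interval (seven words) and the instruction to discontinue infliximab (two words).
- The singular steroid becomes plural in the re-taper sentence.

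Words in common, in order: 73 − 1 − 9 − 1 = 62. Adding back what is particular to colitis: 62 + 2 + 1 = 65, so every difference is accounted for. Only the nine-word gap changes the timing.

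**2. Whether the grammar allows another reading.** One could try to attach the symptom-relief phrase to the taper alone. It does not fit, because the conjunction that introduces the taper comes after the phrase. The phrase therefore modifies the infliximab treatment.

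**3. The rest of the colitis row.** Patients who do improve on steroids already have their own instruction in this row: taper, with no infliximab. The last bullet calls for a surgical consult if symptoms persist after the listed treatment, which assumes that infliximab was available while symptoms were unresolved. The sentence after the disputed one also links infliximab to deterioration: "If symptoms worsen during steroid reduction, initiate a retapering of steroids starting at a higher dose of" "80 or 100 mg followed by a more prolonged taper with or without administration of infliximab". That sentence concerns a later relapse, so it is only weak support on first use.

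**4. Other second-line steps in Appendix A.** The hepatitis table adds a second agent on steroid failure: "If serum transaminase levels do not decrease 48 hours after initiation of systemic steroids, oral mycophenolate mofetil 500 mg every 12 hours may be given". The myocarditis table does the same: "add in infliximab, mycophenolate mofetil or anti-thymocyte globulin if symptoms do not promptly respond to steroids". These are other organs, partly with other agents, so they show the general pattern and do not settle the colitis timing.

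**5. Corrections elsewhere.** None was found. Sections 2.4.1.1 and 7.5 and Table 7-1 all lead back to Appendix A.

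**The case against.** The strongest points on the other side are these.

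- **The origin is unproven.** The missing run begins just after one occurrence of infliximab and ends with the next. A skip between two identical words leaves a grammatical sentence with no visible gap, so a fault in reading the PDF cannot be excluded from the text alone. An author's copying slip explains it equally well. This stands, and it is why the source must be checked before anything is amended.
- **Early infliximab is not prohibited.** Section 7.4.2 exempts treatment of immune-related events from the ban on immunosuppressive drugs, and Section 7.4.1 leaves medication needed for the patient's welfare to the investigator's discretion, provided it does not interfere with KN046. This stands too. It limits the practical effect but does not correct the instruction.
- **The intent can be inferred.** The failure condition comes first in the sentence, the drug is only to be considered, the patient is in hospital, and a surgical consult closes the row. Appendix A also describes itself as general principles. All true, and it keeps the point minor. However, the table gives specific hours, doses and taper lengths, and its reader should not have to repair it.

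**Conclusion.** The concern holds. As written, the colitis step contradicts its own trigger, and the pneumonitis row shows that symptom relief is the condition for stopping infliximab. The error is one sentence in one table cell: 1 of the 4 second-line steps in Appendix A (pneumonitis, colitis, hepatitis, myocarditis).

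It is minor. The documents give no usable rate of Grade 3 or higher colitis, or of steroid-refractory colitis, so the number of patients affected cannot be estimated. KN046 handling is unchanged: the drug is withheld in this row and stopped permanently if Grade 3 or higher colitis is confirmed. Design, sample size and error rates are untouched. The conclusion assumes that the text as read matches the source PDF.

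**What to change.** First check the cell against the source PDF. If the wording is confirmed, amend it to this effect: when symptoms have not eased after 48 to 72 hours on steroids, consider infliximab; once symptoms are relieved, stop infliximab and begin the steroid taper of 6 to 8 weeks. Keep the existing caution about bowel perforation and sepsis. Whether to add a dose and interval, as the pneumonitis row does, is for the sponsor to decide.

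The cost is one corrected table cell by amendment and notice to the single site. Nothing in the design or analysis changes.

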**Table 16-3 Management of immune related endocrinopathies**

CTCAE v5.0 Grade	KN046 Management	Dosing	Action and Guidelines	Diagnostic Consideration
Grade 1-2 

• Hyperthyroidism

• Hypothyroidism

• Thyroid disorder

• Thyroiditis

	

• No change in KN046 dose

		

• Monitor thyroid function or other hormone level tests and serum chemistries more frequently (every 3~6 weeks) until returned to baseline values or clinically stable

• Replacement of thyroid hormone or thyroid suppression therapy as clinically indicated

	All attempts should be made to rule out other causes such as brain metastases, sepsis, and/or severe infection
Grade 3-4 

• Hyperthyroidism

• Hypothyroidism

• Thyroid disorder

• Thyroiditis

	

• Withhold KN046 treatment until on stable replacement dose as determined by resolution of symptoms and normalization of hormone levels

		

• Consider endocrine consultation

• Replacement of thyroid hormone or thyroid suppression therapy as clinically indicated

	
Grade 1-4 

• Adrenal insufficiency

• Hypophysitis

• Hypopituitarism

• Pan-hypopituitarism

	

• Withhold KN046 treatment until on stable replacement dose as determined by resolution of symptoms and normalization of hormone levels

		

• Consider endocrine consultation

• Thyroid hormone and/or steroid replacement therapy to manage adrenal insufficiency

• If Grade 1~2 hypophysitis is considered, pituitary gland imaging should be considered (magnetic resonance imaging [MRIs] with gadolinium and selective cuts of the pituitary can show enlargement or heterogeneity and confirm the diagnosis)

• If adrenal crisis occurs (Grade 3~4 hypophysitis with clinically significant adrenal insufficiency and hypotension, dehydration, and

	

		electrolyte abnormalities, such as hyponatremia and hyperkalemia), it requires hospitalization and intravenous methylprednisolone should be initiated	
--	--	---	--

**Table 0** *Management of immune related hepatitis*

CTCAE v5.0 Grade	KN046 Dosing Management	Action and Guidelines	Diagnostic Consideration
Grade 1 

ALT or AST>1-3 x ULN

Subjects with baseline ALT or AST increased, toxicity Grading worsened for <math>\leq 1</math>

	

No change in KN046 dose

	

Weekly monitor liver function tests

	All attempts should be made to rule out other causes such as medications (eg, statins, antibiotics), alcohol history, viral infections (eg, anti-HAV/HBV/HCV antibody, HEV PCR), other liver diseases (eg, anti-ANA / SMA / LKM / SLA / LP / LCI, iron studies) or metastasis / clot
Grade 2 

ALT or AST 3-5 x ULN

Subjects with baseline ALT or AST increased, toxicity Grading worsened for <math>\leq 1</math> and <math>\leq 5</math> x ULN

	

Withhold KN046

	

Monitor liver function tests every 3 days

If no improvement in liver function tests, treat with oral steroids (prednisolone 1 mg/kg/ day)

	
Grade 3-4 

ALT or AST >5 x ULN

With or without total bilirubin increased > 3x ULN

	

Discontinue KN046

	

Liver biopsy to establish etiology of hepatic injury, if necessary

Treat with high-dose IV prednisolone 2 mg/kg/day or equivalent for 24~48 hours. When symptoms improve to Grade 1 or less, a steroid taper with oral prednisone at 1~2 mg/kg/day (or equivalent) should be started and continue over no less than 4 weeks

	

		
 
• If serum transaminase levels do not decrease 48 hours after initiation of systemic steroids, oral mycophenolate mofetil 500 mg every 12 hours may be given. Caution: infliximab is not recommended due to its potential for hepatotoxicity
 
• Several courses of steroid tapering may be necessary as symptoms may worsen when the steroid dose is decreased
 
	
--	--	---	--

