##### **4.2 Inclusion Criteria**

1. Signed informed consent form;
2. Male or female, 18 years of age or older; willing and able to complete all required procedures of study;
3. Pathologically confirmed diagnosis of thymic carcinoma; a tumor sample is required for confirmation of pathological diagnosis and further studies on the tumor tissue (see correlative science Section 9)
4. Inoperable or metastatic disease;
5. Progressive disease documented in the last 6 months
6. Has failed platinum-based chemotherapy, with progression either during or after treatment
7. Had failed at least one regimen of systemic therapy containing immune checkpoint blockade therapy targeting PD-1, PD-L1, or CTLA-4 for locally advanced unresectable or metastatic disease. Subjects should have documented progressive disease while or after an immune checkpoint therapy. If subjects discontinued therapy due to reasons other than progressive disease, subjects should have completed at least 2 cycles of immune checkpoint therapy
8. Baseline measurable disease according to RECIST 1.1. Target lesions situated in a previously irradiated area are considered measurable if progression has been demonstrated in such lesions;
9. ECOG performance status of 0 or 1;
10. Adequate organ function assessed within 7 days prior to first trial treatment:
  - Hematological function
    - i. ANC $\geq$ 1.5 x 10^9/L;
    - ii. Hemoglobin $\geq$ 9 g/dL;
    - iii. Platelets $\geq$ 100 x 10^9/L;

- Renal function
  - i. Calculated creatinine clearance $\geq$ 60 mL/min (Cockcroft-Gault method);
- Hepatic function
  - i. Total bilirubin $\leq$ 1.5 x ULN (or 2.5 x ULN for documented Gilberts' syndrome);
  - ii. ALT/AST $\leq$ 3.0 x ULN (or 5.0 x ULN for documented liver metastasis);
- INR or aPTT  $\leq$ 1.5 x ULN;

11. Have a life expectancy of at least 3 months;
12. If female of childbearing potential, have a negative serum pregnancy test within 7 days prior to first trial treatment;
13. If female of childbearing potential or a male subject with a partner with childbearing potential, be willing to use a highly effective method of contraception (with a failure rate of less than 1.0% per year) from first study treatment to 24 weeks after completion of the trial treatment.

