## 7.3 Dose modifications

KN046 will be withheld for  $\geq$  Grade 3 drug-related toxicity, including laboratory abnormalities with the exception of laboratory abnormalities that are not clinically significant or that do not meet the criteria of adverse event, and severe or life-threatening AEs (i.e. anemia grade 3, lymphocytopenia grade 3-4, hypercholesterolemia grade 3-4, hypertriglyceridemia grade 3-4).

If a dose of KN046 is withheld due to toxicity, subjects may resume dosing with KN046 when toxicity has improved to  $\leq$  Grade 1.

In case toxicity does not resolve to Grade 0-1 within 12 weeks after last infusion, trial treatment will be discontinued. With the agreement between investigator and Sponsor Medical Monitor, subjects with a laboratory adverse event at Grade 2 after 12 weeks may continue treatment only if asymptomatic and controlled, for example, hypothyroidism or Type 1 diabetes controlled by replacement treatments.

Subjects who require corticosteroids to manage drug-related adverse events must be at an equivalent dose of  $\leq 10$  mg per day of prednisone to resume dosing with KN046. In case of an inability to reduce the corticosteroid dose for managing a drug-related adverse event to the equivalent of  $\leq 10$  mg prednisone per day within 12 weeks of last KN046 dose, patient will go off treatment.

For a subject who experiences a recurrence of the same serious adverse event at the same grade or greater after rechallenge of KN046, study medication will be discontinued.

In addition, if any of below drug-related adverse events occur, KN046 treatment will be permanently discontinued:

- $\geq$  Grade 3 immune related pneumonitis;
- Recurrence of  $\geq$  Grade 2 immune related pneumonitis lasting  $\geq$  4 weeks after appropriate medical interventions;
- $\geq$  Grade 2 immune related CNS toxicities lasting  $\geq$  4 weeks after appropriate medical interventions;
- $\geq$  Grade 3 immune related colitis;
- $\geq$  Grade 3 uveitis or optic neuritis;
- $\geq$  Grade 3 immune related hepatitis with ALT/AST  $> 8 \times$  ULN OR TBIL  $> 3 \times$  ULN;
- $\geq$  Grade 3 immune related nephritis or renal dysfunction.
- $\geq$  Grade 2 myocarditis
- $\geq$  Grade 2 myositis

**Table 7-1** *Guideline on KN046 dose modification*

Toxicity	Grade	Withheld treatment	Resume treatment	Dose / schedule for resuming treatment	Discontinuation of treatment
Hematological toxicity	1, 2	No	Not applicable	Not applicable	Not applicable

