	3 (except for isolate event of grade 3 neutropenia)	Yes			

Toxicity	Grade	Withheld treatment	Resume treatment	Dose / schedule for resuming treatment	Discontinuation of treatment
	4	Yes	Toxicity resolves to $\leq$ Grade 1 or baseline within 12 weeks of last KN046 dose	Resume at planned dose and increase the dose interval by 1 week at each occurrence	Permanent discontinuation if toxicity does not resolve to $\leq$ Grade 1 or baseline within 12 weeks of last KN046 infusion
Non-hematological toxicity with the exception for alopecia of any Grade and Grade 2 fatigue which will be treated as Grade 1 adverse reaction (with the exception of those reported in 7.3)	1	No	Not applicable	Not applicable	Not applicable
	2	Yes	Toxicity resolves to $\leq$ Grade 1 or baseline within 4 weeks of last KN046 dose	Resume at planned dose and dose interval	Permanent discontinuation if toxicity does not resolve to $\leq$ Grade 1 or baseline within 12 weeks of last KN046 infusion
			Toxicity resolves to $\leq$ Grade 1 or baseline beyond 4 weeks and within 12 weeks of last KN046 dose	Resume at planned dose and increase the dose interval by 1 week at each occurrence	
	3, 4	Yes	Toxicity resolves to $\leq$ Grade 1 or baseline within 12 weeks of last KN046 dose	Resume at planned dose and increase the dose interval by 1 week at each occurrence	Permanent discontinuation if toxicity does not resolve to $\leq$ Grade 1 or baseline within 12 weeks of last KN046 infusion; Permanent discontinuation should also be considered for any life-threatening or severe adverse reactions

Note: if increased Grade 3 or 4 CPK occurs, myocardial enzymes (CPK, CK, Tn1, TnT) should also be measured. KN046 will be permanently discontinued in case of elevation on treatment-related myocardial enzymes
					

Infusion related reactions, hypersensitivity reactions, and immune related adverse event should be handled according to the guidelines provided in Sections 7.5.1 and Appendix A, respectively.

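### For immune-related hepatitis with ALT/AST above 5 and up to 8 × ULN, Appendix A stops KN046 while Section 7.3 allows resumption; for raised baselines the Appendix A rows may also overlap

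*Combined protocol and SAP*

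**What the plan says.** **Appendix A, table on immune-related hepatitis**
- Grade 1 (ALT or AST >1–3 × ULN): no dose change, liver tests weekly. A second bullet covers "Subjects with baseline ALT or AST increased, toxicity Grading worsened for" ≤1, with no upper limit in ULN.
- Grade 2 (3–5 × ULN): withhold, liver tests every 3 days. The same baseline bullet appears, again with ≤1, but capped at 5 × ULN.
- Grade 3–4 (>5 × ULN): discontinue, "With or without total bilirubin increased" above 3 × ULN.

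**Section 7.3**
- Drug-related toxicity of Grade 3 or more is withheld. "If a dose of KN046 is withheld due to toxicity, subjects may resume dosing with KN046 when toxicity has improved to" Grade 1 or less.
- The permanent-stop list includes Grade 3 or higher events: "Grade 3 immune related hepatitis with ALT/AST" above 8 × ULN or TBIL above 3 × ULN.
- Table 7-1, in its rows for "Non-hematological toxicity with the exception for alopecia of any Grade" (and some other exceptions), withholds at Grade 2. At Grades 3–4 it withholds, then resumes at a longer interval if the event resolves within 12 weeks. It adds that a permanent stop should be considered for severe reactions.
- The text after Table 7-1 says that "immune related adverse event should be handled according to the guidelines provided in Sections 7.5.1 and Appendix A, respectively".

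**Elsewhere**
- Section 2.4.1.1: "Management of irAEs include withholding KN046 until resolution of toxicity to Grade 1 or less".
- Section 4.2, criterion 10, admits ALT/AST up to 3.0 × ULN, "or 5.0 x ULN for documented liver metastasis".

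**The concern.** These are live dosing rules for a known toxicity of the drug. In KN046-AUS-001 one dose-limiting toxicity at 5 mg/kg every 2 weeks, the dose used here, was a Grade 3 hepatic abnormality without a bilirubin rise (Section 2.3.2.1.1). Normal bilirubin is where the two stop rules can part. Its ALT/AST value is not given, so it cannot be placed in the disputed range.

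If one physician follows Appendix A and another follows Section 7.3, the same liver result leads to a permanent stop or to re-dosing. One error exposes a patient to further liver injury. The other ends treatment in a population for which Section 2.3.1 says there is no standard of care. If the rows of the hepatitis table overlap as well, patients who enter with raised enzymes could be given two different dosing instructions and two different testing frequencies for one value.

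**Working it through.** The plan gives no figure to reproduce, so the check sets the printed rules side by side and runs example values through them.

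**1. Stop threshold.** Appendix A stops if ALT/AST >5 × ULN. Section 7.3 mandates a stop if the hepatitis is Grade 3 or more and ALT/AST >8 × ULN or TBIL >3 × ULN. A value above 5 × ULN is taken as Grade 3 or more, as in the Appendix A table.

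| ALT/AST (× ULN) | TBIL (× ULN) | Appendix A | Section 7.3 |
|---|---|---|---|
| 5.5 | 1 | discontinue | withhold, may resume |
| 6 | 1 | discontinue | withhold, may resume |
| 8 | 2 | discontinue | withhold, may resume |
| 8.5 | 1 | discontinue | permanent stop |
| 6 | 3.5 | discontinue | permanent stop |

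For values above 5 × ULN, the rules differ only where ALT/AST is at most 8 × ULN and TBIL is at most 3 × ULN. This result does not depend on any doubtful sign.

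**2. Row overlap.** Grades are taken from the table's own bands (>1–3, 3–5, >5 × ULN).

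| Baseline → current (× ULN) | Grades worse | Rows met, Grade 1 sign ≤1 as printed | Rows met, Grade 1 sign read as no worsening |
|---|---|---|---|
| 2 → 4 | 1 | Grade 1 (no change) and Grade 2 (withhold) | Grade 2 only |
| 4 → 6 (liver metastasis) | 1 | Grade 1 (no change) and Grade 3–4 (discontinue) | Grade 3–4 only |
| 2 → 6 | 2 | Grade 3–4 only | Grade 3–4 only |

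Both baselines can be enrolled: 2 × ULN in any patient, 4 × ULN with documented liver metastasis.

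The Grade 1 sign decides the matter. Reading the Grade 2 sign as ≥1 instead of ≤1 changes neither example. Reading it as >1, and also letting the baseline bullets replace the absolute bands, removes the 2 → 4 clash but not the 4 → 6 clash.

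**3. Size.** Listed immune-related liver terms of Grade 3 or more at 5 mg/kg every 2 weeks were ALT increased in 1 of 30 and hepatic function abnormal in 1 of 30 in KN046-AUS-001 (Table 2-4). That is 1 or 2 patients of 30, since one patient may have both. In KN046-CHN-001 there were none among 45 (Table 2-10). Neither table gives ALT/AST as a multiple of ULN or by baseline, and no document says how many patients will enter with raised enzymes. The step from these counts to patients in the disputed cells cannot be made.

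**The case against.** The best defence is that Section 7.3 is a floor and Appendix A the operative rule. The permanent-stop list is introduced as an addition and is not said to be exhaustive; resumption is permitted, not required; and Table 7-1 tells the investigator to consider stopping for severe reactions. Someone who discontinues at 6 × ULN breaches nothing in Section 7.3. Appendix A is also stricter than the list elsewhere: it stops for myocarditis from Grade 1 (the list says Grade 2) and for Grade 2 nephritis persisting beyond 7 days (the list says Grade 3). The routing sentence then points the same way.

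Much of this stands. A reader might infer that the protocol is silent on which section governs; the routing sentence does not support that. But the Section 7.3 line is itself about immune-related hepatitis. If Appendix A governs, the 8 × ULN limit does nothing; if it does not, resumption at 6 × ULN is allowed. Appendix A also presents itself as general principles only, which weakens it as an override.

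On the rows, a reader might infer that the table is proven contradictory. It is not. The same ≤1 appears in both bullets of a machine-read table, which may be a typing or extraction fault, and with a different Grade 1 sign both examples fall in one row. The column is headed by CTCAE v5.0, whose handling of raised baselines the documents do not give. Even as printed, Section 2.4.1.1, Section 7.3 and Table 7-1 lean towards withholding, and a careful investigator would probably do so.

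**Conclusion.** The threshold mismatch is an error in the plan as written. It is minor and bears on patient safety and consistent dosing. It rests on the two printed limits alone: for ALT/AST above 5 and up to 8 × ULN with TBIL at or below 3 × ULN, two actions have support in the protocol, with Appendix A the better-supported one.

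The row overlap is conditional. It holds for raised-baseline patients who worsen by one grade if the source table confirms the Grade 1 sign and if grades are counted by the table's own bands.

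A reader might go further and predict a number of affected patients, or expect an effect on the primary result. The documents support neither. The inputs for a count are missing. The Simon two-stage limits and the response definition do not refer to these rules, and Section 8.1 keeps patients who stop for toxicity under tumor assessment.

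**What to change.** **Threshold.** Change the Section 7.3 hepatitis line to the Appendix A limit: permanent stop at ALT/AST >5 × ULN with or without raised bilirubin, keeping TBIL >3 × ULN as a stop. Repeating the bilirubin criterion in the Grade 3–4 row would make the two places read alike. This needs sponsor medical sign-off. Cost: a patient above 5 and up to 8 × ULN loses the option to resume.

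**Rows.** Check both ≤1 signs against the source table. If the Grade 1 sign is confirmed, add two statements:
- when a value above baseline meets more than one row, the more restrictive action applies;
- a value at or below an eligible raised baseline needs no dose change.

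Then 2 → 4 × ULN is withheld, 3.1 → 4.9 is withheld (it lies in the 3–5 band), 4 → 6 is discontinued, and an unchanged 4 continues.

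The cost is mainly some additional held doses, with two cases for the medical reviewer. With liver metastasis, a small rise from 4.9 to 5.1 × ULN becomes a stop. And if the Grade 2 sign is also ≤1 and a rise within a grade counts, 1.5 → 2.5 × ULN would be withheld. If that is not intended, the Grade 2 bullet should require a full grade of worsening.

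The whole change is one table and one line, with no statistical cost.
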